3.3.6. Quarterly Contact Target Dates

The targets dates for the quarterly contacts are 90 days after HCT (Quarterly Contact 1), 180 days after HCT (Quarterly Contact 2), 270 days after HCT (Quarterly Contact 3), and 365 days after HCT (Final Study Visit).

3.3.7. Least-Frequent Clinician-Recommended Monitoring Interval Category

The least-frequent clinician-recommended monitoring interval category summarizes the least-frequent monitoring interval category between discharge from transplant center and each quarterly contact. This is defined from least frequent to most frequent on the Visit Documentation eCRF as "No Further Monitoring Required" < "Quarterly" < "Monthly" < "Bi-weekly" < "Weekly" and participants will be categorized as such. Clinician-recommended CMV monitoring intervals of "Other" will not be considered for determining the least-frequent clinician-recommended monitoring interval category but will be included in Listing 14.

If a participant withdraws consent or dies prior to a quarterly contact or the final study visit, then their lastobserved clinician-recommended prior to withdrawal of consent or death will be used to categorize their leastfrequent clinician -recommended monitoring interval which will be carried forward for the remainder of the study.

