11 STATISTICAL CONSIDERATIONS

11.1 Study Outcome Measures

11.1.1 Primary Endpoint

The primary endpoint will be the proportion of subjects who complete >90% of their recommended CMV monitoring tests by 1-year post-transplant. We will use logistic regression modeling to compare this proportion between subjects randomized to DBS testing versus standard office-based testing. Since randomization will be stratified by transplant site and subject's perceived ease of access to blood draw facility, these factors will be used as adjustment factors in the models.

For each subject, the number of CMV monitoring tests performed will be assessed and the percent of recommended tests will be calculated. Subjects with percent completion >90% will be considered a success with regard to the primary endpoint. The personspecific denominator for the proportion, number of expected CMV monitoring tests, will be variable and dependent on subjects' immunosuppression and hospitalizations during the study. For example, subjects in this study that are highly immunosuppressed a weekly monitoring schedule is generally recommended, often throughout the first year after transplantation. If such a subject were discharged from the primary transplant center at day 100, there would be 38 remaining tests until day 365 after HCT (if the subject is still alive at 1 year). We will assess the actual number of tests performed and calculate the percent of tests (e.g. 36/38 = 94.7%). Another scenario would be for a subject that stopped monitoring and was then re-started on high-dose steroids for treatment of GVHD with resumption of weekly testing, resulting in yet another denominator. Study participants in the DBS arm who are hospitalized during the study should not collect DBS samples while admitted. Rather, admitting hospitals should monitor participants for CMV with plasma CMV DNA PCR testing as recommended for their level of immunosuppression. Those inpatient testing timepoints will not be included in the person-specific denominator.

The primary analysis will be an intent-to-treat (ITT) analysis of all subjects randomized. Another key analysis will be the modified intent to treat analysis of all subjects who had at least one test done after discharge from the primary transplant team.

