14. LOCAL PROVIDER CARE EVALUATION

The number of participants in each intervention group receiving pre-emptive therapy for CMV disease, as well as the mean and standard deviation of viral load at time of the decision to initiate pre-emptive therapy, by transplant site and participants' perceived ease of access to blood draw facility, as well as overall, will be summarized (Table 41).

At each quarterly contact, the least-frequent clinician-recommended monitoring interval recorded for each participant up until 90 days post-HCT (first contact), 180 days post-HCT (second contact), 270 days post-HCT (third contact) and 365 days post-HCT (final contact) will be categorized as described in Section 3.3.7.

The number and proportion of participants in each of the groups between enrollment and the first, second, third and final contacts will be summarized by intervention group, as well as by stratification variables and overall (Table 42, Table 43, Table 44, and Table 45). Note that University of Minnesota results will be excluded from the perceived ease of access stratification as this site recorded actual number of clinician-recommended CMV monitoring tests completed instead of the clinician-recommended CMV monitoring intervals.

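### SAP Tables 42–45 classify participants by the least frequent interval recommended since discharge, so a return to more frequent monitoring cannot show, and a different rule applies after death or withdrawal

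*SAP*

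**What the plan says.** SAP 3.3.7 defines the variable: "The least-frequent clinician-recommended monitoring interval category summarizes the least-frequent monitoring interval category between discharge from transplant center and each quarterly contact". The categories run from no further monitoring (lowest) through quarterly, monthly and bi-weekly to weekly (highest). Intervals recorded as Other are left out.

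The same section covers participants who leave before a contact. Their "lastobserved clinician-recommended prior to withdrawal of consent or death will be used to categorize their leastfrequent clinician -recommended monitoring interval", and this is a category "which will be carried forward for the remainder of the study".

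SAP 14 sets the contacts at 90, 180, 270 and 365 days after transplant, each window running up to that day. It describes Tables 42–45 as follows: "The number and proportion of participants in each of the groups between enrollment and the first, second, third and final contacts will be summarized". So 3.3.7 starts the window at discharge and section 14 starts it at enrollment.

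Both documents provide for frequency rising again. Protocol 11.1.1 gives the case of "a subject that stopped monitoring and was then re-started on high-dose steroids for treatment of GVHD with resumption of weekly testing". SAP 3.3.4, rule 3, says how expected tests are counted after an increase. SAP Appendix 4 Example 3 goes from weekly to bi-weekly and back to weekly.

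**The concern.** Exploratory outcome 8 is to describe local recommendations on monitoring interval. Tables 42–45 are the only planned summary of those recommendations by category and over time, and four tables at successive contacts will be read as a time course.

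For anyone under follow-up, a worst-since-discharge category can stay level or fall but cannot rise, and no further monitoring is a state that a participant cannot leave. Re-escalation by clinicians would therefore be missing from the tables, and stable practice with some switching back and forth would look like steady de-escalation.

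The carry-forward sentence adds a second problem. It assigns the last interval, whereas everyone else receives the minimum. One column would then hold two definitions, with nothing in the table shell to separate participants still followed from those who died or withdrew.

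**Working it through.** **1. The SAP's own example, reproduced.** Appendix 4 Example 3: transplant 1 March 2020, discharge 1 May 2020, bi-weekly from 1 November 2020, weekly again from 20 January 2021, end 1 March 2021.

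- First interval: floor((184 + 1)/7) = floor(185/7) = 26 tests, the last on 30 October.
- Second interval: 30 October to 20 January is 82 days (the SAP prints 80); floor(82/14) = 5, and floor(80/14) is also 5.
- Third interval: floor(40/7) = 5.
- Total: 26 + 5 + 5 = 36, as the SAP states.

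**2. The 3.3.7 rule applied to that participant.**

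| Contact | Date | Least frequent since discharge | In force on the date |
|---|---|---|---|
| Day 90 | 30 May 2020 | Weekly | Weekly |
| Day 180 | 28 Aug 2020 | Weekly | Weekly |
| Day 270 | 26 Nov 2020 | Bi-weekly | Bi-weekly |
| Day 365 | 1 Mar 2021 | Bi-weekly | Weekly |

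Bi-weekly testing was in force from 1 November to 20 January: 30 + 31 + 19 = 80 days. Discharge to end of study is 304 days, and 80/304 = 26%. Weekly testing was in force for the final 40 days.

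**3. The protocol's stop-and-restart case.** The protocol gives no dates. Assume a stop at day 150 and a restart at day 200. The interval in force at days 180, 270 and 365 is none, weekly, weekly. The 3.3.7 category is no further monitoring at all three.

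**4. Direction in a fixed cohort (illustration only).** Assume that in each window an independent share p of a fixed cohort is on less-than-weekly testing, so that actual practice is constant. The share shown below weekly after k windows is 1 − (1 − p)^k. Take Tables 43, 44 and 45 as k = 1, 2, 3:

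- p = 10%: 10, 19, 27%
- p = 20%: 20, 36, 49%
- p = 30%: 30, 51, 66%

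The documents give no switching rates. These figures show the direction of the effect, not its expected size.

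**5. Direction while participants are still entering (illustration only).** Discharge is generally near day 100 and the enrolment window is day 60–180, so many participants enter after the day-90 table. Assume 20 of 100 are discharged by day 90, 20% of those are already bi-weekly, and the other 80 enter on weekly. The weekly share is 16/20 = 80% in Table 42 and (16 + 80)/100 = 96% in Table 43. With 10 to 50 early discharges and 10–30% of them bi-weekly, the share is 70–90% at day 90 and 85–99% at day 180. Here it rises.

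**6. The carry-forward rule.** Assume weekly, then bi-weekly from day 150, weekly again from day 200, and death on day 230. The day-180 category is Bi-weekly. Read literally, 3.3.7 then assigns the last-observed interval, so the day-270 and day-365 categories are Weekly. A survivor with the same history up to day 230 stays Bi-weekly in both tables.

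**The case against.** The case for leaving the tables alone has real content.

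- **The titles disclose the rule.** Each says least frequent, by a given day. That is true, but disclosure does not make the table answer outcome 8, which asks what clinicians recommended.
- **Re-escalation is recorded elsewhere.** SAP 4.5.3 also refers this outcome to 3.3.4 and 3.3.5, Tables 14–19 give the number of recommended tests per participant, and Listing 13 gives each interval with the day it was set. This stands in part: the information is not lost. However, a test count does not show the interval at each contact, and Listing 13 is line data.
- **Nothing inferential depends on it.** This stands in full. The adherence denominator is built from dated intervals and has its own rule for increases.
- **Example 3 is a counting exercise.** This also stands. It shows that the rule misdescribes such a participant, not how often such participants occur.
- **The start-date mismatch is mostly wording.** The eCRF records schedules from discharge onward, so the two starting points may give the same result.

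A reader might infer that the weekly share can only fall across all four tables, whatever clinicians do. The documents do not support that. The one-way property holds per participant under follow-up. Late entry can raise the percentage between Tables 42 and 43, the share stays level if nobody steps down, and the last-observed sentence lets a category rise after death or withdrawal. A reader might also infer that the dead are counted as monitored. They are not: the tables count recommendations, not tests performed, and the carried category may be no further monitoring.

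**Conclusion.** The point holds, as a cheap improvement to a descriptive exploratory summary. For a participant under follow-up, Tables 42–45 cannot show a return to more frequent monitoring, and the SAP's own Example 3 would be misdescribed at day 365. Randomization is allowed only up to day 180 and takes place when discharge is imminent, so the cohort is nearly fixed from Table 43 on. Tables 43–45 therefore lean toward apparent de-escalation to the extent that participants re-escalate. That extent cannot be estimated from the documents. Tables 42 and 43 describe different sets of people and should not be read as a trend.

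Separately, the two rules in 3.3.7 conflict whenever the last interval before death or withdrawal is not the least frequent one, and must be reconciled. The primary and secondary adherence results are unaffected.

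**What to change.** In SAP 3.3.7 and 14:

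- For days 180, 270 and 365, tabulate the interval in force on the target date among participants discharged, alive and still enrolled on that date. Show deaths and withdrawals as separate rows.
- Restrict Table 42 explicitly to participants discharged by day 90.
- Keep the least-frequent category, or the share of person-time in each interval, as a supplement. Compute the category as the minimum up to death or withdrawal, so that one definition applies to everyone.
- Use one start date in both sections; discharge and enrollment must be reconciled.
- Correct the reference for Other intervals: 3.3.7 points to Listing 14, which is concomitant medications, while the intervals are in Listing 13.

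The effective dates are already on the Visit Documentation eCRF, so no new data are needed. The University of Minnesota did not record recommended schedules (SAP 3.3.4), so its column needs the existing footnote under either definition. The cost is SAP wording, table programming and one additional set of tables if the least-frequent version is kept.

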3.2.3. Exploratory Outcome Measures

- 1. Mean time from scheduled pick-up at participant residence (DBS tests) or blood draw facility (plasma sample) to arrival at the laboratory (hours) at all applicable test points throughout the study period
- 2. Number of mobile technology failures, sample collection failures, sample delivery failures, and sample viability failures.
- 3. Sensitivity, specificity and predictive values of CMV detection in DBS versus plasma testing
- 4. Number and type of key transplant characteristics in randomized participants and observational participants
- 5. Describe the baseline participant demographics of randomized cohort and observational cohort.
- 6. Number of participants with end-organ CMV disease (possible and proven/possible) at 1 year after HCT in randomized participants and observational participants
- 7. Describe local provider CMV treatment viral load treatment thresholds
- 8. Describe local provider CMV monitoring interval recommendations
- 9. Report composite scores of different variables of participant and provider satisfactions according to the 5-point Likert scale questionnaires.

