3.3.4. Number of Clinician-Recommended CMV Monitoring Tests Expected

At discharge, the clinician-recommended CMV monitoring schedule is anticipated to be weekly, however during the course of the study the participant's clinical team may recommend that monitoring become less frequent, for example at bi-weekly, monthly, quarterly or other schedules. The recommended monitoring schedules and the dates on which they come into effect are entered into the data system on the Visit Documentation electronic Case Report Form (eCRF) at discharge, each quarterly contact, or as needed between quarterly contacts, during medical chart abstraction. Letting *d* represent the number of days between clinician recommended CMV monitoring tests in the new schedule, the number of expected tests will be calculated using the following assumptions:

- 1. The first expected test occurs d days after discharge.
- 2. If the monitoring frequency is reduced, then the first test for the next schedule is expected d days after the last expected test in the previous interval.
- 3. If the monitoring frequency is increased, then the first test for the new schedule is expected d days after the date that the recommended interval was changed.

The number of expected tests during the study period for a given participant is the sum of the number of expected tests during each monitoring schedule over the course of the study period (defined in Section 3.3.2). Detailed information for the calculations of the number of expected tests can be found in Appendix 4.

At the University of Minnesota, the clinician recommended CMV monitoring schedule was not recorded, so this site entered the actual number of monitoring tests instead. These data will be used for the primary adherence analysis in the ITT population. A sensitivity analysis will be conducted to exclude all participants from the University of Minnesota for the primary and secondary adherence measures along with the local provider CMV monitoring interval recommendations summary (See Section 6.4, Section 8, and Section 14 for further details).

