All Randomized (N = X)	No Further Monitoring Required	XXX	XX.X	xxx	xx.x	xxx	xx.x	xxx	xx.x	xxx	xx.x	xxx	xx.x	xxx	xx.x
	Weekly	XXX	XX.X	xxx	XX.X	xxx	xx.x	xxx	XX.X	xxx	XX.X	xxx	XX.X	xxx	XX.X

	Least-Frequent Clinician- Recommended Monitoring Interval	Transplant Site										se of Access ing Univers			ity
Treatment Arm		Clinician- Recommended Cancer Research Center							MD Anderson Cancer Center		isy	Difficult		Ove	erall
		n	%	n	%	n	%	n	%	n	%	n	%	n	%
	Bi-Weekly	xxx	xx.x	xxx	xx.x	xxx	xx.x	XXX	xx.x	XXX	xx.x	xxx	xx.x	xxx	xx.x
	Monthly	xxx	xx.x	xxx	xx.x	xxx	xx.x	XXX	xx.x	XXX	xx.x	xxx	xx.x	xxx	xx.x
	Quarterly	xxx	XX.X	xxx	XX.X	XXX	XX.X	XXX	XX.X	XXX	XX.X	XXX	xx.x	xxx	XX.X

N=Number of participants in the ITT Population with recommended in-office CMV monitoring intervals recorded.

n = Number of participants with results reported for the clinician-recommended CMV monitoring intervals, excluding monitoring intervals of "Other".

^aThe University of Minnesota entered the actual number of clinician-recommended CMV monitoring tests instead of the expected number of clinician-recommended CMV monitoring tests.

Tables with similar format:

[figure not shown]
- Table 43:Least Frequent Clinician-Recommended Interval Categories by 180 Days Post-HCT, by Intervention Group and Stratification
Variables
- Table 44:Least Frequent Clinician-Recommended Interval Categories by 270 Days Post HCT, by Intervention Group and Stratification
Variables
- Table 45:Least Frequent Clinician-Recommended Interval Categories by 365 Days Post-HCT, by Intervention Group and Stratification
Variables

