16.3.1 Physician Recommended Monitoring Interval Data

Listing 13: 16.3.1 Primary Physician Recommended CMV Monitoring Intervals

[Implementation Note: In the CSR, Participant ID should be USUBJID (not PATID) for purposes of de-identification. Listing should be sorted by Intervention Group, Participant ID, Visit and Date CMV Monitoring Interval Defined. If "Other" is specified for the recommended monitoring interval, then display "Other: [SPECIFY]" where [SPECIFY] is the text entered in the "If Other, specify:" field.]

Intervention Group	Participant ID	Transplant (Study Day)	Enrollment (Study Day)	Visit (Study Day)	CMV Monitoring Interval Defined (Study Day)	Recommended Monitoring Interval
[e.g. DBS, SOC]		XXX	XXX	XXX	XXX	[e.g. Weekly, Biweekly, Monthly, Quarterly, Other:[SPECIFY]]

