APPENDIX 4. WORKED EXAMPLES OF NUMBER OF EXPECTED TESTS

For a given participant, the number of expected tests is derived based on the start dates of the intervals as follows:

Notation:

- 1. Let $t_{i,0}$ denote the date of discharge for participant *i*
- 2. Let $c_i \in \{0, 1, ...\}$ denote the number of times participant *i*'s recommended monitoring interval was changed by their primary care physician during the study period, defined for each participant as the time from enrollment to the earlier of Protocol Completion and Early Termination.
- 3. Let $t_{i,1}, ..., t_{i,c_i}$ denote the times at which the recommended monitoring interval was changed for participant *i*. $t_{i,1}$ is the end date of the initial interval for participant *i*.
- 4. Let t_{i,c_i+1} denote the end of the monitoring period for participant *i*. This is the earlier of the end of the study period or the date after which recommended monitoring is no longer required.
- 5. Let $d_{i,1}, ..., d_{i,c_i}$ denote the corresponding number of days between recommended monitoring tests when the recommended frequency is changed at times $t_{i,1}, ..., t_{i,c_i}$. The days $d_{i,j}$ take the value 7 if recommended frequency is weekly, 14 if the frequency is bi-weekly, 30 if the frequency is monthly and 90 if the frequency is quarterly, 3.5 if the frequency is twice a week, and 17.5 if the frequency is every 2-3 weeks. The initial recommended monitoring frequency should be weekly so the number of days between tests, $d_{i,o}$, should be 7.
- 6. Let $I_{i,j}$ denote the recommended monitoring interval for the j^{th} change to the recommended frequency for participant *i*. The recommended monitoring interval(s) for participant *i* are therefore

$$I_{i,0} = [t_{i,0}, t_{i,1}], I_{i,1} = (t_{i,1}, t_{i,2}], \dots, I_{i,c_i} = (t_{i,c_i}, t_{i,c_i+1}]$$

The number of expected tests in the first interval is calculated as follows. It is assumed that the first expected test is $d_{i,0}$ days after $t_{i,0}$. Let $n_{i,0}$ denote the number of expected tests during $I_{i,0}$. Then,

$$n_{i,0} = floor\left(\frac{t_{i,1}-t_{i,0}+1}{d_{i,0}}\right).$$

Let $m_{i,0}$ denote the date of the last expected recommended monitoring test for participant *i* during interval I_{i0} . Then,

 $m_{i,0} = t_{i,0} + d_{i,0} n_{i,0}.$

There are two possibilities for changes in the monitoring frequency:

1. Frequency in interval $I_{i,j}$ is less frequent than in $I_{i,j-1}$, i.e. $d_{i,j} > d_{i,j-1}$

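### The least-frequent recommended interval ignores 'Other' entries, so a participant relaxed from weekly to every 2-3 weeks can be shown as Weekly in exploratory Tables 42-45

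*SAP*

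**What the plan says.** SAP 3.3.7 defines an ordered category from five named options: no further monitoring, quarterly, monthly, bi-weekly and weekly. Each participant receives the least frequent one recorded between discharge and each quarterly contact. Intervals of 'Other' "will not be considered for determining the least-frequent clinician-recommended monitoring interval category" and are sent to a listing. The footnote to Table 42 (SAP Appendix 1, Local Provider Care Data) also leaves 'Other' out of n, and Tables 43-45 share that format.

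SAP 3.3.4 expects off-category schedules. It says "At discharge, the clinician-recommended CMV monitoring schedule is anticipated to be weekly", but that less frequent testing may follow, "for example at bi-weekly, monthly, quarterly or other schedules". Appendix 4 converts each schedule to days: 7, 14, 30 and 90 for the named ones, then "3.5 if the frequency is twice a week, and 17.5 if the frequency is every 2-3 weeks".

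Tables 42-45 serve exploratory outcome 8 in SAP 3.2.3: "Describe local provider CMV monitoring interval recommendations". SAP 4.5.3 says this outcome will be reported using 3.3.4, 3.3.5 and 3.3.7.

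**The concern.** Every 2-3 weeks and twice a week are not among the five named categories, and Listing 13 provides an 'Other' field with free text. So these schedules almost certainly reach the database as 'Other'. The SAP can place both on a numerical scale and does so for the adherence denominator, yet the interval summary discards them.

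Discarding an entry from a least-frequent rule does not leave the participant unclassified. It returns the next least frequent named entry, and since the starting schedule is anticipated to be weekly, that will often be Weekly. At stake is whether Tables 42-45 describe local recommendations correctly, by arm, site and ease of access.

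**Working it through.** **Inputs.** The category order and the exclusion come from SAP 3.3.7, the day values from Appendix 4 item 5, and the exclusion from n from the Table 42 footnote.

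**The SAP's own figure first.** Appendix 4 Example 2 is weekly from May 1, 2020, then bi-weekly from November 1, 2020, to March 1, 2021.

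- First interval: floor((184 + 1)/7) = floor(185/7) = 26, with the last weekly test on October 30, 2020.
- Second interval: floor(122/14) = 8.
- Total: 26 + 8 = 34, as stated. The SAP prints 120 days where the calendar gives 122; the floored count is 8 either way.

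**The same history with every 2-3 weeks in place of bi-weekly.** The second interval becomes floor(122/17.5) = 6, giving 26 + 6 = 32. So the adherence denominator takes account of the 17.5-day schedule.

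**The 3.3.7 rule on example histories.** Remove 'Other', then take the least frequent named category.

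| History up to a contact | Longest interval (days) | Label under 3.3.7 | Label if ranked by days |
|---|---|---|---|
| Weekly, then bi-weekly | 14 | Bi-weekly | Bi-weekly |
| Weekly, then every 2-3 weeks | 17.5 | Weekly | Every 2-3 weeks |
| Weekly, bi-weekly, then every 2-3 weeks | 17.5 | Bi-weekly | Every 2-3 weeks |
| Weekly, every 2-3 weeks, then monthly | 30 | Monthly | Monthly |
| Weekly and twice a week | 7 | Weekly | Weekly |
| Every 2-3 weeks only | 17.5 | Dropped from n | Every 2-3 weeks |
| Twice a week only | 3.5 | Dropped from n | Twice weekly |

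The first two rows show the inversion: the participant with the longer interval (17.5 against 14 days) receives the more intensive label.

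**Direction.** Removing entries before taking the least frequent can leave the result unchanged or move it to a more frequent category, never to a less frequent one. Among classified participants the error therefore runs one way. The last two rows show that losses from n have no fixed direction: dropping participants tested only every 2-3 weeks removes relaxed schedules, while dropping those tested only twice a week removes intensive ones.

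**Cross-reference.** SAP 3.3.7 sends the 'Other' entries to Listing 14, which is Concomitant Medications. The intervals are in Listing 13, which SAP 8 cites correctly.

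**The case against.** The strongest defence is that the exclusion is openly stated, repeated in the table footnote, and backed by a participant-level listing of the raw entries. The tables are descriptive, with no test attached. The problem is also narrow. Twice-weekly entries cannot change the label when Weekly is also recorded. Every 2-3 weeks matters only while no monthly, quarterly or no-further-monitoring entry has been recorded, and where Bi-weekly is already recorded the shift is only from 14 to 17.5 days. All of this stands and limits the size of the point. It does not make the Weekly label true, and the listing that 3.3.7 names is the wrong one.

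Three stronger readings are tempting, and the documents do not support them.

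- *A reader might infer that these are the only tables showing whether recommended intensity differs by arm.* Tables 14-19 report the number of recommended tests per participant by arm, built under 3.3.4 and Appendix 4 with the 17.5- and 3.5-day values. SAP 4.5.3 also cites 3.3.4 and 3.3.5 for this outcome.
- *A reader might size the error by turning the label into a test count.* On the Example 2 dates, weekly throughout gives floor(305/7) = 43, against the 32 derived above. But a least-frequent category is not a whole-period schedule, and no planned analysis uses it as one. The correct label fails the same comparison: floor(305/17.5) = 17, not 32. The gap says nothing about the rule.
- *A reader might infer that the tables as a whole must look too intensive.* That holds only for classified participants, because losses from n can go either way.

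**Conclusion.** The point holds as a minor defect in a descriptive summary. The stated rule can give a wrong label, and it can place a more relaxed schedule in a more intensive row than a less relaxed one. The effect is confined to exploratory Tables 42-45. The primary and secondary adherence analyses and the recommended-test counts in Tables 14-19 are not affected.

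The conclusion rests on one assumption: that every 2-3 weeks and twice a week are entered as 'Other'. The case report form is not in the documents, but they show no other slot for these schedules. The documents do not say how many participants have such entries, so the size in the tables cannot be computed. It would be nil if every participant with such a schedule also had a less frequent named category recorded by each contact.

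**What to change.** - In SAP 3.3.7, rank 'Other' entries that can be converted by their Appendix 4 day values.
- In Tables 42-45, add a row for every 2-3 weeks (between Bi-weekly and Monthly) and a row for twice weekly (more frequent than Weekly).
- Exclude only entries that cannot be converted to days, and report their number.
- Amend the Table 42 footnote to match.
- Change the reference in 3.3.7 from Listing 14 to Listing 13.

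The cost is a few lines of SAP text, two table rows and a small programming change. The mapping already exists in Appendix 4, and no new data are needed.
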